**7.2.12. Deaths**

- Deaths – all causes  
A fatality (of any cause).
- Malaria attributed deaths (including *P. falciparum* malaria)  
A fatality for which malaria (including *P. falciparum* malaria) is listed as a contributing cause of death.
- *P. falciparum* malaria attributed deaths  
A fatality for which
  - Malaria is listed as a contributing cause of death
  - And the malaria type is identified as *P. falciparum*.
- Deaths attributed to an AE
- Deaths attributed to an AESI
- Meningitis attributed death

*Of note, as cause of death is a free text reported by the investigator on the Study Conclusion form, a specific guideline explaining the process to retrieve the above categories was prepared (EPI-MALARIA-002 VS AME (115055) General study information study specific coding term retrieval and supply for MedDRA coding\_version 2.0\_20190108)*

Number of outpatient visits per centre

The number of outpatient visits per centre will be computed as the sum of outpatient visits that occurred for the children enrolled in the same centre.

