9.2.5.8. Deaths

- Deaths – all cause
A fatality (of any cause).
- Malaria attributed deaths (including *P. falciparum* malaria)
A fatality for which malaria (including *P. falciparum* malaria) is listed as a contributing cause of death. This is based on verbal autopsy using the INDEPTH Standard Verbal Autopsy Questionnaire* [[INDEPTH](#), 2003] for children who died at home or medical judgment/medical records for children who died at a primary health care facility or hospital.
- Deaths attributed to an AE
A fatality for which an AE is listed as a contributing cause of death, based on either verbal autopsy using the INDEPTH Standard Verbal Autopsy Questionnaire* [[INDEPTH](#), 2003] for children who died at home or medical judgment/medical records for children who died at a primary health care facility or hospital.

* If a site is not part of the INDEPTH network, or does not have an equivalent surveillance system in place, the INDEPTH procedures for verbal autopsy might be implemented to ensure consistency across study sites.

Deaths, including malaria attributed deaths with an uncertain diagnosis and outcome after review by the GSK safety physician will be reviewed by the expert panel to confirm the primary/secondary cause of death (see Section [9.2.7.4.4](#)).

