As part of good medical practice enrolled children presenting at health facilities (outpatient and inpatient) with signs and symptoms of SAEs (see Section 11), are expected to receive appropriate diagnostic testing and care by clinical staff following standard care in the country (see Section 9.2.7.5).

9.2.7.4.4. *Case ascertainment for other AE leading to hospitalisation or death*

Other AE leading to hospitalisation or death with an uncertain diagnosis and outcome after review by the GSK safety physician will be reviewed by the external panel of experts. These cases will be flagged in the eCRF during the manual cleaning by the GSK safety physician, for external expert review. Two selected experts will independently review the cases. They will be provided with all available medical information (e.g. medical and family history, physical examination, clinical presentation/picture, laboratory results, concomitant medication/vaccination and any other relevant information identified in patient medical records) and classify the cases. Anonymized copies of the medical records including laboratory results and technical examinations may be requested by the experts. If the two experts cannot reach an agreement, then the different clinical opinions of the experts will be listed. This final classification will be used for the statistical analyses.

9.2.7.4.5. *Case ascertainment for malaria*

Enrolled children presenting at health facilities (outpatient and inpatient) with signs and symptoms of malaria will receive malaria testing (RDT and/or microscopy) as part of standard care in the country (see Section 9.2.7.5). As part of good medical practice the clinical staff will ensure that all subjects diagnosed with malaria will receive adequate care following national guidelines.

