### **6.9.2. Co-primary endpoints**

#### **6.9.2.1. AESI**

- Each AESI will first be analysed separately after case ascertainment on confirmed cases (hospitalised cases) classified by MedDRA SOC and PT level and case definition, and grouped by body system overall:
  - According to principal investigator (PI) diagnosis (i.e. after first line laboratory ascertainment or second line laboratory if available) **for progress report (see section 6.9.3.1) and interim analysis**,
  - According to final diagnosis (external expert diagnosis or PI diagnosis if external expert diagnosis not available) **for interim and final analysis**.
- Note: The confirmed AESI cases are those AESI with an available ICD-10 code (i.e. variable ICD-10 code not equal to “Not confirmed”, as per convention in the case report form [CRF] guidelines).*
- AESI will also be grouped by body system as described in table 3 of the protocol:
  - Nerves and central nervous system: Acute Disseminated Encephalo-Myelitis (ADEM), encephalitis, Guillain-Barre Syndrome, Hypotonic Hyporesponsive Episode (HHE), general convulsive seizure
  - Hepato-gastrointestinal and renal system: intussusception, hepatic failure or renal insufficiency
  - Skin and mucous membrane, bone and joints system: juvenile chronic arthritis, Stevens-Johnson syndrome/toxic epidermal necrolysis, Henoch-Schonlein purpura, Kawasaki disease
  - Systemic diseases and haematology: diabetes mellitus type I, thrombocytopenia, anaphylaxis

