## 6.9.3. Incidence of co-primary endpoints

### 6.9.3.1. Description of the events

The occurrence of the following endpoints will be regularly (every 6 months) reported in progress reports [[Progress Report](#)] on the total enrolled cohort for hospitalised cases and outpatient visits when applicable:

- Each AESI according to site diagnosis,
- Other AE leading to hospitalisation or death, according to site diagnosis
- First line laboratory meningitis diagnosis according to site diagnosis following protocol definition (i.e. Bacterial confirmed meningitis, probable meningitis, clinically suspected meningitis).
- Malaria cases reported during outpatient visit or at hospital:
  - Clinically diagnosed Malaria
  - Any uncomplicated malaria (including *P. falciparum* malaria)
  - Any severe malaria (including *P. falciparum* malaria)
  - Severe *P. falciparum* malaria
  - Severe *P. vivax*
  - Cerebral malaria

- Fatal malaria cases
- Death reported at hospital or at home classified by MedDRA PT from study conclusion.

The number of subjects (%) reporting at least once each endpoint as well as the total number of events listed above and the number of associated outpatient visits/hospitalisations will be presented for both AS and EHS by EPI vaccination status and by gender. MedDRA SOC and PT level will be displayed for those safety endpoints.

Progress reports will include individual listings and statistical tables. The same tables and listings will also be presented for the final report.

Descriptive data in the progress report will also be presented:

- The demographic census will be presented by study site and by age group according to gender and overall.
- The number of subjects enrolled will be presented by study site, by study group and according to EPI vaccination status.
- The evolution of enrolment will be presented separately for each study group.
- Population characteristics (age at informed consent, gender) will be described by study group according to EPI vaccine received.
- The number and percentage of subjects who received the EPI vaccine doses will be summarised for EPI vaccinated subjects by each study group according to gender and overall.

And descriptive analysis of quality indicators (see section 6.10.7) will be done:

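### SAP 7.2.12 takes cause-specific deaths from the investigator's free text and gives no step by which the expert panel's cause replaces it, although the protocol requires the panel's classification to be analysed

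*SAP*

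**What the plan says.** **Protocol.** Section 9.2.5.8 defines malaria-attributed and AE-attributed deaths by whether the condition is listed as a contributing cause. The basis is verbal autopsy for deaths at home and medical judgment or records for deaths at a facility. Deaths whose diagnosis and outcome remain uncertain after the sponsor's safety physician has looked at them, malaria-attributed deaths included, "will be reviewed by the expert panel to confirm the primary/secondary cause of death". That sentence refers to section 9.2.7.4.4, where two experts review each flagged case independently. The section ends: "This final classification will be used for the statistical analyses". If the experts differ, the rule is: "If the two experts cannot reach an agreement, then the different clinical opinions of the experts will be listed".

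**SAP.** Section 7.2.12 lists the death categories: all-cause, malaria, *P. falciparum* malaria, AE, AESI and meningitis. It describes the source in these words: "as cause of death is a free text reported by the investigator on the Study Conclusion form". To sort that text into the listed categories, the SAP relies on a separate document and reports that "a specific guideline explaining the process to retrieve the above categories was prepared". Section 6.9.3.1 uses the same source in its list of described endpoints: "Death reported at hospital or at home classified by MedDRA PT from study conclusion". It adds that "The same tables and listings will also be presented for the final report".

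For the diagnoses of AESI and of other AEs, the SAP states a hierarchy in sections 6.9.2.1 and 6.9.2.2: "According to final diagnosis (external expert diagnosis or PI diagnosis if external expert diagnosis not available". Neither 7.2.12 nor 6.10.5 (causes of hospitalisation and death) repeats it for causes of death.

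**The concern.** The protocol names the cause to be analysed for an uncertain death that has been reviewed: the panel's. The SAP names a different source and says nothing about the panel. An analyst who programs the death categories from 7.2.12 has no instruction to look at the panel's result.

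What is at stake is limited but real. Causes of death, overall and by gender, and malaria-attributed mortality, overall and by gender, are stated secondary objectives (Protocol 8.2). Malaria mortality is also among the events to be compared with EPI-MAL-003 (Protocol 9.1.1). The panel sees the deaths whose cause is least certain, and Protocol 9.9 itself calls cause-of-death ascertainment a concern because of the limits of verbal autopsy. If the panel's result is not used, its review does not improve the figures it was meant to protect.

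**Working it through.** The plan gives no figure to reproduce, so the check is a comparison of texts.

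1. **Which deaths does the protocol rule reach?** Only those still uncertain after the safety physician's review (9.2.5.8). For all other deaths, a cause reported by the investigator from verbal autopsy or medical records fits the protocol definition, and the SAP is consistent with it.

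2. **What does the protocol require for those deaths?** The panel confirms the primary or secondary cause, and the final classification goes into the analyses (9.2.5.8 with 9.2.7.4.4). Where the two experts disagree, their opinions are listed and no analysis rule is given.

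3. **What does the SAP do?**
   - Section 7.2.12: investigator's free text, sorted into categories by a separate guideline. No panel step is stated.
   - Section 6.9.3.1: deaths at hospital and at home are classified from study conclusion, and those tables are carried into the final report.
   - Section 6.10.5: the malaria species for malaria deaths comes from outpatient and hospitalisation visits. That is a second source for species, not for whether malaria was a cause.

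4. **Does another part of the SAP supply the missing step?**
   - Section 6.9.2.2 gives the expert diagnosis precedence for other AEs leading to hospitalisation or death, but it is worded for hospitalised cases. It does not clearly reach deaths at home, nor the malaria, AESI and meningitis death categories. Section 7.2.12 places AE-attributed deaths on the free-text route.
   - Section 6.10.4 lists death among endpoints confirmed by final diagnosis. That concerns the risk-factor models, and Tables 5 and 6 limit the death model to all-cause death, where the cause does not matter.
   - The last paragraph of section 6.9.3.1 limits the final analysis to confirmed cases under the protocol case definitions. This points towards the protocol but names no source for the cause of death.

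5. **Is a departure declared?** SAP section 9 lists changes on risk-factor models for other AEs, EPI-MAL-005 variables, missing data and terminology. The source of the cause of death is not among them.

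6. **Size.** The number of deaths placed in a different category equals the number of deaths reviewed by the panel multiplied by the share in which the panel's cause changes the category. Neither factor is in the documents. The result is zero if the panel never changes a category and cannot exceed the number of reviewed deaths. All-cause counts and rates do not change.

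**The case against.** The strongest reply is that the SAP is silent rather than contradictory. The retrieval guideline cited in 7.2.12 is not in the public documents and could give the panel's cause precedence. Sites might also correct the study conclusion form after the panel has reported. Further, the SAP says its endpoints follow the protocol, and section 6.9.3.1 ties the final analysis to protocol case definitions.

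Part of this stands. A reader might infer that causes overruled by the panel will certainly be counted; with the guideline unseen, the documents do not support that. They support only that the SAP states no override. Neither document says that the guideline contains one or that the form is corrected, and a general reference to the protocol does not tell a programmer which field to use.

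Three other inferences should not be drawn:

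- *That the unlabelled Death block in Table 5 shows a deliberate choice of the investigator's diagnosis.* The blocks for hospitalisation, anaemia and febrile convulsions also lack the final-diagnosis label.
- *That a home death recorded as malaria, for which the panel names sepsis, must leave the malaria count under the protocol.* Malaria need only be a contributing cause. The death leaves the count only if the panel removes malaria altogether.
- *That the panel settles every uncertain death.* It confirms causes, and unresolved disagreements are only listed.

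**Conclusion.** The point holds as an unreconciled difference between protocol and SAP. For deaths reviewed by the panel, the protocol requires the final classification to be analysed. The SAP derives cause-specific deaths from the investigator's text, states no replacement step and declares no departure. Following the SAP as written therefore departs from the protocol's rule.

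The effect is confined to panel-reviewed deaths and to cause-specific results. All-cause mortality and the all-cause death model are unaffected. A reader might want a percentage of misattributed deaths, but any such figure would rest on two invented inputs, so none is given.

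The conclusion assumes that the unseen guideline does not already give the panel's cause precedence. If it does, the remaining defect is that the SAP does not say so.

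**What to change.** - In SAP 7.2.12, state that malaria, AE, AESI and meningitis attributed deaths use the panel's primary or contributing cause where the panel reviewed the death, and the study-conclusion cause otherwise. This extends the SAP's own hierarchy for AESI and other AEs to deaths.
- State that the study-conclusion cause also applies where the two experts do not agree, since the protocol gives no analysis rule for that case.
- Label the Death block of Table 5 to match.
- Show the investigator-only version of the cause-specific death results as a sensitivity analysis. The difference between the two would give the size that cannot be worked out now.

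If the guideline already contains this rule, one sentence in 7.2.12 saying so covers the first item. If the investigator's cause is intended throughout, declare and justify that in SAP section 9.

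The cost is small: SAP wording, plus linking the panel's classifications to the death records. The documents do not say how the panel's causes of death are stored, so the effort of that link should be checked.

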### 7.2.13. Last contact date

The last contact date will be derived as:

- For deceased subjects the last contact date will be set as the death date.
- For subjects who have finished their participation in the study and for whom their participation did not finish prematurely (i.e. “Did the study participant finish its participation in the study prematurely” equal No) the last contact date will be set as the last contact date from study conclusion CRF page
- For the other subjects (i.e. “Did the study participant finish its participation in the study prematurely” not equal No) the last contact date will be defined as the latest date among:
  - Date of consent
  - Date of reconsent
  - Last date of hospitalisation
  - Last discharge date of hospitalisation
  - Last check-up after discharge
  - Last date of outpatient visit
  - Last home visit
  - Date of enrollment of EPI-MAL-003 study
  - ***Date of RTS,S/AS01E vaccine***
  - Date of migration (From Study continuation or from Study conclusion)

Notes:

- The last contact date recorded in study conclusion CRF page will not be used for this scenario (i.e. when “Did the study participant finish its participation in the study prematurely” not equal No).
- The last contact date will not be computed using start and end date of symptoms associated with events

In addition:

- For subjects enrolled with protocol amendment 4 or subjects enrolled with protocol amendment 3 and who signed the ICF addendum related to protocol amendment 4, the last contact date should not be after the child reaches 5 years ***or 44 months follow-up after visit 1 of the last child enrolled in AS per site whichever comes first:***
  - ***Kombewa: 7 April 2022***
  - ***Kintampo: 27 April 2022***
  - ***Navrongo: 19 July 2022***

- For subjects enrolled with protocol amendment 3 who did not sign the ICF addendum related to protocol amendment 4 (meaning that the reason for not signing the addendum is different than “Study participant enters directly with Protocol Amendment 4”), the last contact date should not be after the child reaches 3 years or 24 months follow-up per site whichever comes first:
  - Kombewa: 25 January 2018*
  - Kintampo: 7 February 2018*
  - Navrongo started directly under protocol amendment 4*

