In the event of death occurring at home, the cause of death will be systematically obtained through verbal autopsy using the INDEPTH Standard Verbal Autopsy Questionnaire [[INDEPTH](#), 2003] as is routinely done in the study area.

If a site is not part of the INDEPTH network, or does not have an equivalent surveillance system in place, the INDEPTH procedures for verbal autopsy might be implemented to ensure consistency across study sites.

CONFIDENTIAL115055 (EPI-MALARIA-002 VS AME)
Protocol Amendment 7 Final**9.2.7.1.12. Study conclusion**

Subjects will exit the study when they reach 5 years of age or at study end (whichever occurs first), if not earlier due to migration or in the event of death.

At the study conclusion (home visit, V10), a record will be taken of the subject's health and vital status, any disabilities and all vaccinations received.

The investigator will review collected data to ensure accuracy and completeness and will complete the Study Conclusion screen in the eCRF.

Note: There might be an overlap of studies EPI-MAL-002 and EPI-MAL-003. Children enrolled in active surveillance of EPI-MAL-002, and not eligible for RTS,S/AS01_E vaccination or declining vaccination will continue to be followed up to the study conclusion visit in EPI-MAL-002. Children enrolled in active surveillance of EPI-MAL-002, and becoming vaccinated with RTS,S/AS01_E will have their study conclusion of EPI-MAL-002. Thereafter, these children can be eligible and enrolled in EPI-MAL-003 according to the inclusion/ exclusion criteria and the EPI-MAL-003 recruitment procedures. For children enrolled in enhanced hospitalisation surveillance of EPI-MAL-002, study conclusion of EPI-MAL-002 will be done at start of study EPI-MAL-003 (as the vaccine becomes available in the study sites that are exposed clusters). Thereafter, these children can be eligible and enrolled in active surveillance or in enhanced hospitalisation surveillance of EPI-MAL-003 according to the inclusion/ exclusion criteria and the EPI-MAL-003 recruitment procedures.

CONFIDENTIAL

115055 (EPI-MALARIA-002 VS AME)
Protocol Amendment 7 Final

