9.7.5. Analysis of co-primary objectives**9.7.5.1. Analysis population**

The population will include the subjects from the active surveillance of the EPI-MAL-002 study.

A secondary population will include the subjects from the active and enhanced hospitalisation surveillance of the EPI-MAL-002 study, computing incidence for all children < 5 years.

9.7.5.2. Statistical approach**9.7.5.2.1. Incidence of AESI, and other AE leading to hospitalisation or death**

The incidence rate of each AESI and other AE leading to hospitalisation or death will be calculated by dividing the number of subjects reporting at least one event over the follow-up period by the total person-time. A 95% CI will be computed using an exact method for a Poisson variable. The at-risk period will follow any dose, with a censoring of subjects when they receive the following dose. The minimum at-risk period for the analyses is 2 weeks. All AESI expected to occur between 0 day and 13 days following

CONFIDENTIAL

115055 (EPI-MALARIA-002 VS AME)
Protocol Amendment 7 Final

dose administration (see [Table 3](#)) will be analysed with an at-risk period of 2 weeks. The at-risk period of 6 weeks will be used for AESI expecting to occur between 14 days and 6 weeks. Finally, at-risk periods of 3 months, and 6 months will be for the AESI expected to occur between 6 weeks and 3 months, and between 3 months and 6 months, respectively. For other AE leading to hospitalisation or death the at-risk period for the analyses will be defined with the support of the GSK safety physicians and the panel of experts. In addition, the distribution of the Time-to-Onset of events after vaccination will be described, and additional at-risk periods will be considered based on the results as sensitivity analyses.

The person-time for an event of interest (e.g. juvenile chronic arthritis) will be calculated as the time between the reference date (date of first administration of DTP/HepB/Hib vaccine or date of first virtual vaccination, corresponding to the week before first visit) and the end of the at-risk period or the earliest of the followings:

- Date of first diagnosis of event of interest (e.g. first episode of juvenile chronic arthritis).
- Date of end of study period.
- Date of enrolment in EPI-MAL-003 (when applicable).
- Date when child reaches 5 years.
- Date of last contact (Lost-to follow-up).
- Date of death.

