**Table 1      Definition of at-risk period for AESI**

AESI	Risk period identified (for other licensed vaccines)*	Risk period applied
ADEM	NA	6 weeks
Encephalitis	6 weeks and 2 weeks	
Guillain-Barre Syndrome	3-5 days to 6-10 weeks	3 months
Generalized convulsive seizures	0-7 days	2 weeks
Hypotonic Hypo responsive Episode	immediately to 48h	2 weeks
Intussusception	1 to 7 days	2 weeks
Hepatic Insufficiency	1-10 days	2 weeks
Renal Insufficiency	1-10 days	2 weeks
Juvenile Chronic Arthritis	≤6 months	6 months
SJS & TEN	1-3 weeks	6 weeks
Henoch Schonlein purpura	NA	6 months
Kawasaki Disease	1 month	6 weeks
Diabetes mellitus type 1	≤6 months	6 months
Anaphylaxis	0-48 hours	2 weeks
Thrombocytopenia	12-25 days	6 weeks

\* from Table 3 of the protocol

Of note:

- The predefined list of AESI with expected at-risk period is available in the current Table 3 of the protocol,
- The at-risk period of 12 months will be used for meningitis,
- For other AEs leading to hospitalisation or death:
  - ***IR will only be computed on the 10 most frequent AEs following the grouping done by the Epidemiologists and a Physician (see section 6.9.2.2).***

- An at-risk period of 7 days and 30 days will be applied. Other risk periods may be defined with the support of the GSK Safety Physicians and the panel of experts.

**Table 2** Follow-up period definition after each dose

Risk period applied	Start	Stop earliest (i.e. date of censoring is whichever occurs first)
2 weeks	Reference date*	
 
• Date of first diagnosis of event of interest
 
• Date of death
 
• Date of next dose
 
• Date of end of risk period
 
• Date of last contact**
 
• Date of migration
 
• Date when child reaches 5 years or end of the study
 

6 weeks		
3 months		
6 Months		
12 Months		

\*Reference date: see definition detailed in section [7.2.2](#)

\*\* Date of last contact: see definition detailed in section [7.2.13](#)

Notes:

- a child may come back into the study after a certain period of lost-to follow-up. In such a case, the person-year will only consider the duration when the child was present on site (e.g. from reference date to migration date, then from immigration date to the end). To do so, a migration date will be derived using migration date from:
  - Date of migration:
    - From Study continuation
    - From Study conclusion
A return date will be derived using return date from:
  - Date of return:

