### 6.11.2. Derivation of incidence rate and prevalence

- For all endpoints listed in **Table 4** incidence rate will be calculated by dividing the number of all cases over the follow-up period by person-year as defined in the table.

If a subject had several cases during the period defined, all episodes will be reported.

The number of person-years will be computed as the sum of subjects follow-up period expressed in years.

**Table 3** Follow-up period definition for other secondary endpoints

Analysis	Start	Stop (earliest)
D3 → D3 + 1Y	Third dose or virtual vaccination*	
 
• One year after third dose
 
• Date of death
 
• Date of last contact**
 
• Date of migration
 
• Date when child reaches 5 years
 

D3 → D4 + 1Y	Third dose or virtual vaccination*	
 
• One year after virtual fourth dose
 
• Date of death
 
• Date of last contact**
 
• Date of migration
 
• Date when child reaches 5 years
 

D3 → D3 + 2Y	Third or virtual vaccination*	
 
• Two years after third dose
 
• Date of death
 
• Date of last contact**
 
• Date of migration
 
• Date when child reaches 5 years
 

D1 → D4 + 2Y	First dose or virtual vaccination*	
 
• Two years after virtual fourth dose
 
• Date of death
 
• Date of last contact**
 
• Date of migration
 
• Date when child reaches 5 years
 

D3 → D4 + 2Y	Third dose or virtual vaccination*	
 
• Two years after virtual fourth dose
 
• Date of death
 
• Date of last contact**
 
• Date of migration
 
• Date when child reaches 5 years
 

\* Virtual vaccination: for 5-17 month study group or unvaccinated children

\*\* Date of last contact: lost-to follow-up

The prevalence rate for anaemia will be computed by dividing the number of all cases by the number of enrolled children.

**Table 4 Incidence rate and prevalence calculations for other secondary objectives (children enrolled in active surveillance)**

Endpoints	Numerator	Denominator

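### Follow-up does not stop at EPI-MAL-003 enrolment or RTS,S vaccination: the SAP uses both dates only inside a latest-date rule

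*SAP*

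**What the plan says.** **Protocol.** Section 9.7.5.2.1 (and the abstract) ends person-time at the close of the at-risk period or at the earliest of a list of dates. One entry is "Date of enrolment in EPI-MAL-003 (when applicable". Section 9.2.7.1.12 gives the order of events. Active-surveillance children "becoming vaccinated with RTS,S/AS01_E will have their study conclusion of EPI-MAL-002", and then "Thereafter, these children can be eligible and enrolled in EPI-MAL-003". Table 4 footnote 7 repeats the link between vaccination and study conclusion. Visit 10, a home visit, takes place at study conclusion.

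**SAP Tables 2 and 3.** Table 2 (co-primary) stops at the earliest of first diagnosis, death, next dose, end of risk period, last contact, migration, and "Date when child reaches 5 years or end of the study". Table 3 (other secondary endpoints) stops at a window limit such as "Two years after virtual fourth dose", death, last contact, migration or age 5 years. Neither table names EPI-MAL-003 enrolment or RTS,S vaccination.

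**SAP 7.2.13.** Last contact has three branches:
- Deceased children: the date of death.
- Children who finished non-prematurely: the contact date on the study-conclusion page.
- Everyone else: "the last contact date will be defined as the latest date among" ten dates. These include last home visit, "Date of enrollment of EPI-MAL-003 study" and the RTS,S date added in SAP Amendment 2. The study-conclusion date is expressly not used here.

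The section does set upper limits: "the last contact date should not be after the child reaches 5 years" or a fixed site date, with earlier limits for children held to Amendment 3. It sets none at the two dates at issue.

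**SAP Section 9** lists four changes from protocol. This is not one of them.

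**The concern.** A protocol stop date has become one element of a maximum. It ends follow-up only if nothing later is recorded. The RTS,S date is in a weaker position, because in the protocol's order it comes before both study conclusion and EPI-MAL-003 enrolment. A Visit 10 or an enrolment after the dose overrides it. So does any other home visit or admission at which staff first learn of the dose.

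The objectives concern incidence before RTS,S implementation, and these rates are the baseline for EPI-MAL-003. Vaccinated time, with any event in it, would be counted as unvaccinated baseline.

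Exposed analyses are the long active-surveillance windows: 12-month meningitis (co-primary), 12-month cerebral malaria, death and hospitalisation, and the Table 3 periods.

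Not exposed are:
- the interim analysis (cut-off 5 October 2018);
- the census denominators for children under 5;
- children held to Amendment 3 (capped in early 2018);
- the 2- and 6-week windows in on-schedule 6-12 weeks children.

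Time in children who stay in EPI-MAL-002 because they are ineligible or decline vaccination is properly unvaccinated time.

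**Working it through.** **1. The plan's own figure.** Protocol Table 6, 12-month window, 10,000 children, one month after each of doses 1 and 2 and 12 months after each of doses 3 and 4:

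PY = 10,000 × (1 + 1 + 12 + 12)/12 = 21,666.67

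Five events give 5/21,666.67 = 23.1 per 100,000 PY, exact Poisson 95% CI 7.5 to 53.9. This reproduces the table; so do its other rows.

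**2. The two rules side by side.** Let W be the window end, E EPI-MAL-003 enrolment, V the first RTS,S dose and C the last other EPI-MAL-002 contact.
- SAP (latest-date branch): min(W, max(V, E, C))
- Protocol: min(W, E, last contact)
- Pre-implementation objective: min(W, V, E, last contact)

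Illustrative dates (assumed), in days after dose 3 with W = 365:

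| V | E | C | SAP | Protocol | Objective |
|---|---|---|---|---|---|
| 100 | 130 | 95 | 130 | 130 | 100 |
| 100 | none | 114 (Visit 10) | 114 | 114 | 100 |
| 100 | 130 | 160 | 160 | 130 | 100 |

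SAP and protocol agree when enrolment is the last recorded date, and differ when a later contact is on file. In none of these cases does the RTS,S date end follow-up.

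**3. Size, prompt conclusion.** Visit 10 has a ±2-week window, and Protocol 9.2.7.1 allows attempts within the month. If Visit 10 falls due at the dose (assumption), the excess is about 2 weeks to 1 month per child.
- Per 100 vaccinated children: 100 × 14/365.25 = 3.8 PY; 100/12 = 8.3 PY. Divided by 21,666.67: 0.02% and 0.04%.
- A 1% change needs 216.7 PY: 216.7/(14/365.25) = 5,653 children at 2 weeks, or 216.7 × 12 = 2,600 at 1 month.
- Primary schedule only: 10,000 × 14/12 = 11,667 PY. A 1% change needs 116.7 PY, that is 3,044 or 1,400 children.
- Outer limit, all 10,000 children of a group at 1 month: 833 PY (3.8%). Expected cases at the five-event rate: 833.3 × 5/21,666.67 = 0.19.

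**4. Who could be affected.** Assume first doses at 5-9 months (Protocol 7.1; country ages are not given) and availability in Q1 2019 at every site (Protocol 7.4). The last Visit 1 is the SAP site date minus 44 months: 7 August 2018 (Kombewa), 27 August 2018 (Kintampo), 19 November 2018 (Navrongo). The SAP does not say which group that child was in, so the ages below are the youngest possible. A 6-12 weeks child is taken as 49 days old at Visit 1, a 5-17 months child as at least 5 months; one month = 30.4375 days.

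| Youngest possible age (months) | Kombewa | Kintampo | Navrongo |
|---|---|---|---|
| 6-12 weeks, 1 Jan 2019 | 6.4 | 5.8 | 3.0 |
| 6-12 weeks, 31 Mar 2019 | 9.4 | 8.7 | 5.9 |
| 5-17 months, 1 Jan 2019 | 9.8 | 9.2 | 6.4 |
| 5-17 months, 31 Mar 2019 | 12.8 | 12.1 | 9.3 |

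Under these assumptions the affected children are mainly late 6-12 weeks enrolees, plus late Navrongo 5-17 months enrolees.

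**5. Which windows are still open.** For an on-schedule 6-12 weeks child (dose 3 at 98 days), closing age = (98 days + window)/30.4375: 3.7 months (2 weeks), 4.6 (6 weeks), 6.2 (3 months), 9.2 (6 months), 15.2 (12 months). A first RTS,S dose at 9 to 5 months of age leaves 6.2 to 10.2 months of the 12-month window open, and 0.2 to 4.2 months of the 6-month window.

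**6. Size, late discovery.** Visits 5 and 6 are 12 months apart. If a dose were first learned of at Visit 6, the SAP rule would count all of the remaining 12-month window. Per 100 such children: 100 × 6.2/12 = 51.7 PY to 100 × 10.2/12 = 85.0 PY, or 0.24% to 0.39% of 21,666.67. How often this happens is not stated.

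**The case against.** - **Last contact is a stop in both tables, and both dates feed it.** True, so they act as indirect stops. They do so only when nothing later is recorded, which depends on the data and is not a rule.
- **On the protocol's sequence, enrolment is the latest date, so SAP and protocol agree.** This stands for a child who follows the sequence. Post-discharge check-ups also run only to study conclusion, so contacts after enrolment should be few.
- **RTS,S vaccination is not in the protocol's stop list.** Correct. Only the enrolment date is a departure from Protocol 9.7.5.2.1. The vaccination stop follows from the objective and from the vaccination-triggered conclusion, and adding it is itself a change that must be declared.
- **The non-premature branch may stop at the right place.** Possibly, since vaccination triggers study conclusion. The documents do not say how such a conclusion is coded, and the branch has no limit at either date.
- **Other documents may settle it.** The SAP cites programming specifications, and Protocol 9.9 defers the switch between studies to the EPI-MAL-003 protocol. Neither is available. If the specifications already apply a cap, the SAP text still needs to say so.
- **The effect is negligible and the exposed group may be smaller.** Largely accepted. Protocol 9.9 says start dates may vary by country. One quarter after 31 March 2019, the youngest possible 6-12 weeks child would be about 11.7 months old at Kintampo and 8.9 at Navrongo. Under the 5-9 month assumption only Navrongo would remain.

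**Conclusion.** The rule is wrong as written, with a small expected effect. The SAP omits a protocol stop date from its person-time tables without declaring it, and places the RTS,S date where it cannot limit follow-up once a later contact exists.

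The likely size is 0.02% to 0.04% of 12-month person-time per 100 vaccinated children, assuming 2 weeks to 1 month each. A dose discovered late would carry more. The total cannot be determined, because the documents give neither the number vaccinated nor the gap from dose to enrolment. Against Table 6's five-event interval of 7.5 to 53.9, effects of this order would not change a conclusion. The case for correcting it is fidelity to the protocol rule and to the pre-implementation objective. It should be fixed before the final analysis.

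**What to change.** 1. Add EPI-MAL-003 enrolment and the first RTS,S/AS01_E dose as separate stop dates in SAP Tables 2 and 3. The first restores the protocol rule; the second matches the objective.
2. In SAP 7.2.13, cap last contact in every branch at the earlier of the two dates, in the form already used there for age and site dates.
3. Do not count later events in these active-surveillance rates.
4. Report how many children are censored at each date.
5. List the RTS,S stop in SAP Section 9 as an addition to Protocol 9.7.5.2.1, with any departure that remains. If the programming specifications already apply the cap, align the SAP text with them.

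The cost is one derivation line and SAP wording, with slightly fewer person-years. Both dates are already inputs to 7.2.13.
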